7.1.2.7 Efficacy Data Point Set 7 (EDPS7)

EDPS7 contains all data collected. A treatment policy strategy will be used for all intercurrent events other than discontinuation from the study which will use a while on treatment strategy (i.e., the collection period will be ended at the time of study discontinuation).

7.1.2.8 Safetyagree Data Point Set 1 (SDPS1)

SDPS1 consists of all observed data collected at a scheduled visit.

7.1.2.9 Safety Data Point Set 2 (SDPS2)

SDPS2 consists of all observed data collected, including data from scheduled and unscheduled visits.

7.2 Covariates and Subgroups

Subgroups based on baseline severity of disease will be defined as follows:

- Using baseline vIGA score of 3 for efficacy analysis
- Using baseline vIGA score other than 3 for summaries only (2, 4)

For the inferential models defined in [Section 9](#), in addition to the baseline vIGA score and relevant baseline score where applicable, the following covariates will be considered:

- Body mass index (<30 kg/m², ≥30 kg/m²)
- Sex (male, female)
- Race (Non-Hispanic white and Hispanic or Non-White)
- Region (North America, Europe, Asia Pacific)

Covariates selection will be done separately for cohorts 1-3 analyses and cohort 4.

7.3 Missing Data

Missing efficacy data such as individual item scores will be dealt with as detailed in [Section 5.3.3](#). Imputation of missing efficacy data due to intercurrent events will be performed in EDPS1, EDPS2, EDPS3, EDPS4 and EDPS5 as described in [Section 7.1.2](#).

7.3.1 Partial Dates/Times

Partial dates and times for AEs, medical conditions and concomitant medications will be imputed for the purpose of assigning study phases and calculating duration. Listings will always include the reported date/time information rather than any imputations.

Partial AE onset and concomitant medication (from concomitant medications CRF page) start dates will be imputed as follows:

- If only the month and year are specified, and the month and year of the start of treatment are not the same as the month and year of the start date, then use the 1st of the month.
- If only the month and year are specified, and the month and year of the start of treatment are the same as the month and year of the start date, then use the date of start of treatment. If this results in a start date after a known or partial end date, then use the 1st of the month.
- If only the year is specified, and the year of the start of treatment is not the same as the year of the start date, then use January 1 of the year of the start date.

- If only the year is specified, and the year of the start of treatment is the same as the year of the start date, then use the date of the start of treatment. If this results in a start date after a known or partial end date, then use January 1 of the year of the start date.
- If the start date is completely unknown, then use the date of the start of treatment. If this results in a start date after a known or partial end date, do not impute the start date.

Concomitant medication (from atopic dermatitis past treatments CRF page) start dates will be imputed as follows:

- If only the month and year are specified, then use the 1st of the month.
- If only the year is specified, then use January 1 of the year of the start date.
- If the start date is completely unknown, then do not impute the start date.

Partial AE onset start times will be imputed as follows:

- If the actual or imputed start date is the same as the treatment start date, and the start time is completely missing, then use the time of start of treatment.
- If the actual or imputed start date is not the same as the treatment start date, and the start time is completely missing, then use 00:00.
- If the actual or imputed start date is the same as the treatment start date, and the start time is partially missing (hh:XX) then use the following:
 - If the hour is the same as the hour of the start of treatment time then use the complete time of the start of treatment (i.e., both hours and minutes)
 - If the hour is not the same as the hour of the start time than use hh:00.
- If the actual or imputed start date is not the same as the treatment start date, and the start time is partially missing (hh:XX) then use hh:00

Partial medical conditions start dates will be imputed as follows:

- If only the month and year are specified, then use the 1st day of the month.
- If only the year is specified, then use January 1st of that year.
- If the start date is completely unknown, do not impute the start date.

Partial AE resolution, medical condition stop dates and concomitant medication (from concomitant medications CRF page) stop dates and date last smoked will be imputed as follows:

- If the event, condition or medication is flagged as ongoing, do not impute the stop date
- If only the month and year are specified, then use the last day of the month.
- If only the year is specified, then use December 31 of that year.
- If the stop date is completely unknown, do not impute the stop date.

Concomitant medication (from atopic dermatitis past treatments CRF page) stop dates will be imputed as follows:

- If the event, condition or medication is flagged as ongoing, do not impute the stop date
- If only the month and year are specified, and the month and year of the screening visit are not the same as the month and year of the end date, then use the last day of the month.
- If only the month and year are specified, and the month and year of the screening visit are the same as the month and year of the end date, then use the date of screening visit.

- If only the year is specified, and the year of the screening visit is not the same as the year of the end date, then use December 31 of that year.
- If only the year is specified, and the year of the screening visit is the same as the year of the end date, then use the date of screening visit.
- If the stop date is completely unknown, do not impute the stop date.

Partial AE resolution and concomitant medication stop times will be imputed as follows:

- If the actual or imputed stop date is non-missing, and the stop time is completely missing, then use 23:59 on that date.
- If the actual or imputed stop date is non-missing, and the stop time is partially missing, then hh:59 for missing minutes.
- If the actual or imputed stop date is missing, do not impute the stop time.

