6.9.1.2. Rescue Therapy

If required, Investigators may prescribe / recommend prescription of rescue therapy for participants experiencing unacceptable worsening of atopic dermatitis. Additionally, individuals with uncontrolled atopic dermatitis could be at risk for a secondary skin infection. These participants may be prescribed an antimicrobial therapy to treat the infection as detailed below. Rescue therapy use is allowed throughout the entire study. There is no limit on the number of times that topical rescue therapy can be prescribed, although Investigators and participants may wish to consider whether the study is suitable for them if repeated courses are required.

Rescue therapy, including antimicrobial rescue therapy, should be prescribed as detailed below, and any specific deviations should first be discussed with the Medical Monitor. Participants rescued by such topical therapy will continue to take IMP and use of rescue therapy will be documented in the participant eDiary ([Section 6.6.1 eDiary](#)). Of note, Investigators should make every attempt to conduct the following assessments immediately prior to administering any rescue therapy, by use of an unscheduled visit, if needed:

- EASI
- vIGA
- PP-NRS
- AEs
- Concomitant Medications

For non-sensitive body sites:

- Moderate potency (grade IV and V – [Appendix 14.2](#)) topical corticosteroids, twice daily for up to 7 days

For sensitive sites e.g., head and neck:

- Topical tacrolimus (0.1%), topical pimecrolimus (1%) or grade VII topical corticosteroid, twice daily for up to 7 days

If topical rescue therapy fails to control symptoms adequately, then the participant should be considered for alternative systemic therapy or phototherapy by the Investigator/their practitioner, at which point they will be classified as a treatment failure and IMP will be discontinued.

For possible skin infection:

- Topical:
 - Appropriate courses of topical antimicrobial therapies, such as fucidic acid cream (e.g., Fucidin), are acceptable for use for skin infections, as required
 - If requiring concomitant moderate potency steroid therapy, fucidic acid with betamethasone 0.1% (as the valerate ester), (e.g., Fucibet cream) twice daily for up to 7 days
- Oral:
 - Appropriate course(s) of oral antibiotic(s) may be prescribed as per clinical need

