5.3.3.14 Rescue Therapy

Rescue therapy use is allowed throughout the entire study: selected topical corticosteroids and calcineurin inhibitors systemic antimicrobials and topical antibacterial may be prescribed. An unscheduled visit will be performed to collect skin assessments prior to administering any rescue therapy, if needed.

Rescue therapy use will be documented as concomitant medication once prescribed and in a daily symptom diary during the whole course. Each rescue therapy course will be recorded in concomitant medication CRF separately, resulting in a one record in a concomitant medication dataset for each course.

Any medications taken during the study and classified as TCS/TCl rescue therapy medications in the sponsor provided spreadsheet with total course duration no more than 8 days (adjusted for dosing

frequency – only days with planned medication usage are counted in course duration) will be considered as rescue therapy with exception for medications which stopped at least 14 days before Day 1 – these cannot be rescue therapy.

For the number of courses of TCS/TCI rescue therapy in Weeks 1-4, 5-8, 9-12, 13-16, course will only be counted at the start day of course. If the rescue therapy course starts in one period and continues to the next period it will be counted only in the first period where the start of the course belongs. The number of courses of rescue therapy will be also evaluated for the whole period of Weeks 1-16.

For the same periods, rescue therapy use will be evaluated. In case of rescue therapy course overlap with the period, the participant will be considered as those who used rescue therapy in this period.

The number of days requiring TCS/TCI rescue therapy in Weeks 1-8, 9-16, 1-16 will be calculated as:

Number of days requiring rescue therapy (days) = min(therapy stop date, the end of the period date) – max(therapy start date, the start of the period date) + 1

In case of multiple rescue therapy medications concurrently, the day still will be counted only once.

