9.3.1 Primary Efficacy Estimand

The primary efficacy estimand will be the effect of each individual EDP1815 cohort compared to the pooled placebo group on the percentage of participants achieving EASI-50 at Week 16. The population summary measure of interest will be the odds ratio between each active EDP1815 treatment group and pooled placebo.

Intercurrent events will be accounted for in the following manner:

Table 1 Intercurrent Event Strategies for the Primary Estimand (EDPS1)

Intercurrent event		
Use* of Permitted TCS/TCI Therapy or Type 1 Prohibited Medications ¹	Study Discontinuation Before Week 16 Visit or Type 2 Prohibited Medications ² Use	Noncompliance or Unblinding or Other Protocol Deviations Affecting Efficacy Before Week 16

If <28 days before Week 16 visit: Composite strategy Participant will be considered a non-responder
 
If ≥28 days before Week 16 visit: Treatment policy strategy Data will be used as collected
	
If type 2 prohibited medication² used: Composite strategy Participant will be considered a non-responder from the date of medication start
 
If due to related** reason: Composite strategy Participant will be considered a non-responder from the time of treatment discontinuation in case of missing data
 
If due to non-related** reason: While-on-treatment strategy No replacement of missing data (data after treatment discontinuation will be used as collected)
	
Treatment policy strategy: Data will be used as collected

* Consider the last day with therapy for participant before Week 16.

** Treatment discontinuation reasons will be checked. Reasons related to study medication are lack of efficacy, treatment failure, adverse event (if related). Also, withdrawal of consent may be considered related to study medication based on the clarification text provided, that will be assessed by the Evelo team and provided in a separate spreadsheet. Non-related reasons are all other reasons.

¹Prohibited concomitant medications which may affect efficacy requiring the concomitant medication to be immediately discontinued where possible once the use is discovered. Such medications use will be recorded as protocol deviation. Classification will be provided by the sponsor in a separate spreadsheet.

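### Partial rescue dates are stretched to month end or month start, so about 93% of 7-day courses with one partial date exceed the 8-day limit and remove the participant from the rescue counts

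*SAP*

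**What the plan says.** SAP 5.3.3.14 records each rescue course as one concomitant-medication CRF record, and SAP 7.1.2 takes rescue for analysis from the CRF although the diary also holds it.

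SAP 7.3.1 states that partial dates "will be imputed for the purpose of assigning study phases and calculating duration". For the concomitant-medications page:

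- Stop date: "If only the month and year are specified, then use the last day of the month".
- Start date, where the month and year of treatment start "are not the same as the month and year of the start date, then use the 1st of the month".
- Start date, where the month and year of treatment start "are the same as the month and year of the start date, then use the date of start of treatment".

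Two rules then use duration. SAP 5.3.3.14 accepts a listed TCS/TCI record as rescue only "with total course duration no more than 8 days", counting planned-use days. SAP 9.4.3.1 drops from the count analyses any participant with a CRF rescue course longer than 8 days, on the ground that the record may be wrong. Protocol 6.9.1.2 sets topical rescue courses at up to 7 days, twice daily.

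The 28-day rule uses a date, not a duration. The footnote to SAP Table 1 reads "Consider the last day with therapy for participant before Week 16". SAP 5.3.2.3 lists TCS/TCI not considered rescue as type 1 prohibited medication, and SAP 9.3.1 and 13 give type 1 the same strategy as rescue. The SAP has no special rule for partial rescue dates, no cap at the permitted course length and no fallback to the diary.

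**The concern.** Month-end and month-start imputation is a general convention that suits long-running medications. Here it is applied to courses of at most a week, which are then tested against a limit one day longer than the permitted course. Almost any missing day breaks the limit.

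The direct stake is in the rescue endpoints. A compliant course stops being rescue, and SAP 9.4.3.1 removes the whole participant from the models for number of courses and days of rescue. Everyone removed in this way is a rescue user, so the exclusion depends on the outcome being counted. A second, conditional stake is the primary endpoint, if a late imputed stop date enters the 28-day rule.

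**Working it through.** **Inputs.** Course length 7 days (Protocol 6.9.1.2); limit 8 days (SAP 5.3.3.14, 9.4.3.1); imputation rules (SAP 7.3.1); 28-day window from last use (SAP 7.1.2.1, 9.3.1). Assumptions: the true day is uniform over a 365-day year, and a partial start date goes to the 1st.

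**Check of the window against the SAP's own example.** SAP 7.1.2.1, Example 2 has rescue on Days 25 to 31. Week 8 is Day 57: 57 − 31 = 26, below 28, non-responder. Week 12 is Day 85: 85 − 31 = 54, as collected. Both match the SAP table.

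**1. Start known, stop partial.** Let shift = month end − true stop. Imputed duration = 7 + shift, which exceeds 8 when shift is 2 or more. Only a true stop on the last two days of a month passes: 2 × 12 = 24 days. Failures: (365 − 24)/365 = 341/365 = 93.4%.

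**2. Stop known, start partial.** Imputed duration = 7 + (day of month of true start − 1). Only starts on the 1st or 2nd pass, so again 341/365 = 93.4%. The last day of use does not move.

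**3. Both partial.** Imputed duration is at least a full month (28 to 31 days), so 100% fail. In the month of treatment start the inflation is smaller, because the start goes to the treatment start date. Such a record can pass if treatment began in the last 8 days of that month (for example the 25th of a 31-day month: 31 − 25 + 1 = 7).

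**4. Shorter courses, one date partial.** Failure share = 1 − 12(9 − L)/365 for length L: 73.7% (1 day), 80.3% (3 days), 86.8% (5 days).

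**5. Size of the stop-date shift.** The mean in a month of M days is (M − 1)/2, that is 13.5, 14.5 and 15.0 for 28, 30 and 31 days. Over the year: (7 × 31 × 15.0 + 4 × 30 × 14.5 + 28 × 13.5)/365 = 5373/365 = 14.7 days, range 0 to 30, never earlier.

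**6. Which courses carry the shift.** The 24 that still pass in step 1 have shifts of 0 or 1 day (total 12). The 341 that fail average (5373 − 12)/341 = 15.7 days.

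**7. If imputed stops feed the 28-day rule.** The flagged span grows from 28 to about 28 + 14.7 = 42.7 days. Of true stops 28 to 111 days before Week 16 (84 days), 14.7/84 = 17.5% would be moved inside the window.

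*Example.* A course runs 8 to 14 March, with the stop recorded as March only. Imputed stop 31 March; duration 31 − 8 + 1 = 24 days; fails. With Week 16 on 20 April, the true gap is 37 days and the imputed gap 20.

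**8. Scale.** The documents give no rate of partial dates. Take 2% to 10% of rescue records as an assumed range.

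- Records failing through one partial date: 0.02 × 0.934 = 1.9% to 0.10 × 0.934 = 9.3% of rescue records.
- Primary endpoint, type 1 route, applying the planned response rates of 25% to 50% (Protocol 11.8) to rescue users: 0.10 × 0.175 × 0.25 to 0.50 = 0.4% to 0.9% of courses truly ending 28 or more days before Week 16; at 2%, 0.1% to 0.2%. Even if all 75 participants in an arm had one such course, 75 × 0.009 is about 0.7 of a participant.

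**The case against.** **Partial rescue dates should be rare.** Rescue is prescribed on study, an unscheduled visit is planned when it starts between visits, diaries are reviewed at each visit, and queries are resolved before lock. Pre-study eczema treatments, where vague dates are more likely, have their own CRF page and date rules. This stands as a limit on size. It does not make the rule right for the records it reaches.

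**SAP 7.3.1 names study phase and duration, not the 28-day rule.** This also stands. Use of imputed dates there is an inference, though the SAP offers no other date. Duration, by contrast, is named outright.

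**A stronger reading is tempting.** A reader might infer that one rescue course both fails the definition and carries a 15-day shift into the primary analysis, producing false non-responders. The documents do not support that. A 7-day course with a known start that remains rescue shifts by 0 or 1 day (step 6), and month-start imputation does not move the last day at all. A large shift reaches the primary endpoint only if the course is classed as type 1 prohibited and imputed dates feed the clock. On that route the 28-day strategy is the same, so failing the rescue definition does not itself change the primary result. If the sponsor's classification spreadsheet does not list the course as type 1, it leaves the 28-day rule altogether, the opposite direction. An imbalance between arms is possible but not shown. Supplementary estimand 5, which counts any use since Day 1, does not depend on the stop date while the record stays rescue or type 1.

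**Bounding by the course length assumes adherence.** SAP 9.4.3.1 itself expects some CRF courses over 8 days. A bounded stop would shorten a course that really ran on, and would favour response in the 28-day rule. This stands, and is why the 28-day date should be shown both ways.

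**Conclusion.** The point holds for duration. Followed as written, SAP 7.3.1 makes 93.4% of 7-day courses with one partial date, and 100% with both partial and the start set to the 1st, exceed the limit in SAP 5.3.3.14. SAP 9.4.3.1 then excludes the participant from the count analyses because of an excess that the imputation created. These are shares of affected records, and rest on days being uniform within the month.

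The effect on the primary endpoint is conditional on type 1 classification and on imputed dates entering the 28-day rule, neither of which the SAP settles. Under the assumed range in step 8 it stays below one participant per arm. The frequency of partial rescue dates is unknown and the trial-level effect may be small. This is a minor but specific and cheap correction.

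**What to change.** For TCS/TCI rescue-list records, add to SAP 7.3.1, 5.3.3.14 and 9.4.3.1:

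- An imputed date may not cause a course to fail the 8-day limit, nor a participant to be excluded from the count analyses.
- For duration, use the daily diary rescue entries first where available. Otherwise bound the imputed date by the protocol course length: stop = earlier of month end and start + 6 days; start = later of the 1st and stop − 6 days. In the March example either bound returns 7 days. If both dates are partial neither bound can be computed, so use the diary or query the site.
- State which date enters the 28-day rule, month end or bounded, and run the other as a sensitivity analysis.

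The cost is a few SAP lines, a small programming change and one extra run. The downside is that a course that truly ran longer, with its stop day missing, would be shortened; the sensitivity run shows how much that matters.

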7.3.2 Adverse Event Information

AEs with missing relationship will be considered 'Related' for summary purposes but recorded as missing in the listings.

7.4 Interim Analyses and Data Monitoring

7.4.1 Purpose of Interim Analyses

Interim analysis

The Interim analysis will be performed to check that no imbalance of treatment groups has occurred due to stratified randomisation leaving multiple incomplete blocks.

If an imbalance is detected, the randomisation schedule may be slightly adapted for the final participants to ensure that all treatment groups have enrolled at least 73 participants.

No other decisions regarding study conduct will be made based on the interim results and the study will not be stopped if superior efficacy or futility is found.

Cohorts 1-3 analysis

After the last patient last visit in cohorts 1-3, DBL and cohorts 1-3 specific analysis will be performed. No decisions regarding the study conduct will be made based on the cohorts 1-3 analyses, but the results may be shared externally. Also, cohorts 1-3 efficacy tables and listings will be considered final and included in CSR at the end of study.

7.4.2 Planned Schedule of Interim Analyses

The interim analysis will be performed after approximately 290 participants have been randomised..

Cohorts 1-3 specific analysis will be performed after the cohorts 1-3 DBL.

7.4.3 Endpoints to be Included in the Interim Analysis

Interim analysis

No endpoints will be evaluated. Only the distribution of participants in each of the treatment groups (Active cohort 1-3 and pooled placebo) will be considered.

Cohorts 1-3 analysis

All analyses planned for the study will be done, but will only include cohorts 1-3 participants.

7.4.4 Adjustment of Confidence Intervals and p-values

Interim analysis

No comparisons of efficacy will be performed so no adjustments for alpha-spending are required.

Cohorts 1-3 analysis

Efficacy tables and figures will be considered final so no adjustments for alpha-spending are required.

